## **Secondary Endpoints**

We will compare the improvement in the severity of AKN symptoms, degree of dyspigmentation, and patient-reported outcomes (DLQI and NRS) between time points (Baseline, 4, 8, and 12 Weeks) and groups (placebo and active) with the nonparametric tests described for the primary endpoint. We will also adjust, for each outcome, a generalized linear mixed-effects model including time, treatment group, their interaction as fixed effects, and a random intercept for each participant. This modeling strategy will decide each outcome's probabilistic distribution and link function based on goodness-of-fit criteria. The Spearman correlation coefficient will measure the association between reduction in lesion counts and improvement in patient-reported outcomes. In addition, we will compare the percent area of the treatment area affected with dyspigmentation (hypo- or hyperpigmentation) at each visit.

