Participants will be followed with visits scheduled at baseline, 4 weeks, 8 weeks and 12 weeks. At each visit, participants will complete surveys regarding the severity of AKN's associated symptoms (pain, pruritus, burning etc.) as well as the dermatology quality of life index (DLQI) and numerical rating scale (NRS) surveys (Appendix B&D). In addition, photographs will also be obtained for global assessment and lesion count will be performed. The investigator will assess the treatment area for any dyspigmentation and document the % area affected within the treatment area at each visit. Tape strips will also be collected from lesional (occipital scalp) and non-lesional (frontal scalp) at Baseline and Week 12. There will be a phone call visit at week 5 to assess tolerance of medication increase and a safety follow-up visit at Week 14. Statistical analysis will be performed. Throughout the length of the study, any adverse events (AEs) related to the treatment will be recorded.

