## **RANDOMIZATION:**

Once a subject meets all the inclusion and exclusion criteria, they will be assigned a randomization number on day 0/baseline. Enrolled subjects will be randomized in a 2:1 ratio of Duobrii to placebo.

The randomization will be performed by designated research staff/personnel at the Icahn School of Medicine using a randomization generator. The subjects and assessors (sub-investigators) will remain blinded to individual treatment assignment during the study. Research staff will also be responsible for blinding of the medication.

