## **DATA ANALYSIS:**

### **Sample Size Considerations**

A sample size of n=20 Duobrii-treated subjects allows 80% power at 5% significance to detect a minimum reduction of 35% in the median number of lesions at week 12 with the one-sided Wilcoxon nonparametric test. This calculation assumes an average count of 15 AKN lesions at baseline and a standard deviation of 7 lesions around the mean difference at week 12, and a drop-out rate of 30%. These numbers are based on data reported by Okoye et al. (2014), who compared lesion counts at week 16 to baseline in a set of 11 UVB-treated subjects. The sample size calculation is based on the asymptotic relative efficiency of the Wilcoxon test compared to paired Student's t-test. A sample size of n=20 treated subjects compared to n=10 placebo-treated ones allows 80% power at 5% significance to detect a minimum 50% difference between proportions of patients with a reduced number of AKN lesions. This calculation is based on the application of a one-sided Z-test for the difference between two independent proportions and also assumes a maximum 30% dropout rate within each arm.

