## **Primary Endpoint**

The primary analysis for the primary endpoint will test for a reduction in lesion counts after 12 weeks of treatment. We will apply the two-sided Wilcoxon test to assess the significance of the difference between pre- and post-treatment median numbers of lesion counts. The secondary analysis will compare the reduction in lesion counts between active and placebo groups after 12 weeks. For this purpose, we will apply the Z-test to verify the hypothesis that the proportions of patients with reduced AKN lesions differ between active and placebo groups. A more comprehensive analysis will adjust a generalized linear mixed-effects model, based on Poisson distribution, including time and treatment group as fixed factors and a random intercept for each subject. This model will include the whole time-course and contrasts of interests will be estimated.

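### The mixed models for the secondary outcomes make no use of the randomised baseline as an adjustment; a common baseline mean or a baseline covariate would sharpen the week-12 comparison at almost no cost

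*Combined protocol and SAP*

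**What the plan says.** Under Data Analysis, Secondary Endpoints, the plan compares symptom severity, dyspigmentation and the patient-reported scores (DLQI and NRS) "between time points (Baseline, 4, 8, and 12 Weeks) and groups (placebo and active". It does so in two ways. The first reuses the nonparametric tests of the primary endpoint. The second, fitted to every outcome in addition, is "a generalized linear mixed-effects model including time, treatment group, their interaction as fixed effects, and a random intercept for each participant". The distribution and link are left open: "This modeling strategy will decide each outcome's probabilistic distribution and link function based on goodness-of-fit criteria".

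The section names no baseline covariate, does not constrain the arms to a common baseline mean, and does not say which contrast will be reported. It gives no effect size, standard deviation, correlation between visits, sidedness or power for any secondary outcome.

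Two other sections matter. Randomization: "Enrolled subjects will be randomized in a 2:1 ratio of Duobrii to placebo". Study Design Overview: "Participants will be followed with visits scheduled at baseline, 4 weeks, 8 weeks and 12 weeks", with the symptom surveys, DLQI, NRS and percent area of dyspigmentation recorded at each visit. So a baseline value exists for every one of these outcomes.

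**The concern.** Because allocation is randomised, the two arms have the same expected baseline score. A model with group, time (including Baseline) and their interaction ignores this and estimates a separate baseline mean in each arm. The week-12 interaction then subtracts the whole of any chance baseline imbalance, whereas the efficient estimate subtracts only the share that carries over to week 12, in proportion to the correlation rho.

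In a trial this small, chance imbalance is common. With 14 and 7 patients, the standard error of the baseline difference is sqrt(1/14 + 1/7) = 0.46 SD. A difference of 0.5 SD or more in either direction would therefore arise in about 28% of trials.

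What is at stake is precision. The hypothesis is worded as a comparison with placebo and covers symptoms and dyspigmentation. Of the tests described for the primary endpoint, the Wilcoxon is pre- versus post-treatment and the between-arm test is on proportions. The mixed models are therefore where a between-arm difference in these scores would be estimated on the full scale.

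**Working it through.** **The plan's nearest figure.** The only power statements concern lesion counts. Twenty treated patients are said to suffice "to detect a minimum reduction of 35% in the median number of lesions at week 12 with the one-sided Wilcoxon nonparametric test". This reproduces:
- 35% of 15 lesions is 5.25, and 5.25/7 = 0.75 SD.
- A one-sided 5% paired t-test at 80% power needs 13.
- Dividing by the Wilcoxon efficiency, 13/0.955 = 13.6, so 14.
- Allowing for 30% dropout, 14/0.70 = 20.

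It says nothing about the secondary outcomes. I take from that section only the arm sizes and the dropout allowance: 20 x 0.70 = 14 active and 10 x 0.70 = 7 placebo.

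**Assumptions, because the documents give no values.** Identity link; equal variance at each visit; a constant correlation rho between visits, as a random intercept implies; complete data in the patients analysed; effect of 1 SD or 0.5 SD at week 12. I use two-sided 5%, as the analysis text does for lesion counts: "We will apply the two-sided Wilcoxon test to assess the significance of the difference between pre- and post-treatment median numbers of lesion counts".

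**Step 1: what the contrast is.** With Baseline as a level of time and a full interaction, the fitted means are the observed arm-by-visit means. The week-12 interaction is then the difference in mean change. Fitting the model to simulated data confirmed this: the interaction and the raw difference in mean change were both -0.47425.

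**Step 2: variances, in units of the score variance.**
- Difference in change: 2(1-rho).
- Baseline-adjusted: 1-rho².
- Ratio: (1-rho²)/[2(1-rho)] = (1+rho)/2, below 1 for every rho under 1.

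This gives 0.65, 0.75 and 0.85 at rho 0.3, 0.5 and 0.7.

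**Step 3: power.** SE = sqrt[v(1/14 + 1/7)], noncentral t, with 19 df for change and 18 for adjusted.

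| Effect | rho | SE, change | SE, adjusted | Power, change | Power, adjusted | Gain (points) |
|---|---|---|---|---|---|---|
| 1 SD | 0.3 | 0.548 | 0.442 | 41.1% | 57.3% | 16 |
| 1 SD | 0.5 | 0.463 | 0.401 | 53.6% | 65.5% | 12 |
| 1 SD | 0.7 | 0.359 | 0.331 | 75.4% | 81.6% | 6 |
| 1 SD | 0.8 | 0.293 | 0.278 | 89.9% | 92.5% | under 3 |
| 0.5 SD | 0.3 | 0.548 | 0.442 | 14.0% | 18.9% | 5 |
| 0.5 SD | 0.5 | 0.463 | 0.401 | 17.7% | 21.9% | 4 |
| 0.5 SD | 0.7 | 0.359 | 0.331 | 26.3% | 29.9% | 4 |

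With all 20 versus 10 patients and a 1-SD effect, power goes from 70.3% to 82.0% at rho 0.5.

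**Step 4: degrees of freedom.** A random-intercept model over four visits pools residual error: 3 x (21-2) = 57 df, not 19. With pooled df on both sides (57 and 56), the 1-SD figures become 43.5% to 60.5%, 56.5% to 68.8% and 78.3% to 84.4%, gains of about 17, 12 and 6 points. If the planned four-visit model is compared instead with a single-visit week-12 ANCOVA on 18 df, the gains fall to about 14, 9 and 3 points.

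**Step 5: simulation.** In 400 simulated trials (14 versus 7, rho 0.5, Gaussian random intercept, four visits), the variance of the week-12 contrast was 0.219 with free baseline means (theory 0.214) and 0.170 with a common baseline mean (theory 0.161). Both were unbiased.

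**The case against.** The strongest reply is that nothing here is wrong. Time, group, interaction and random intercept is a standard longitudinal model. It is unbiased, no inflation of Type I error has been shown, and it does use baseline, as the reference for change. The models sit beside nonparametric tests, on secondary endpoints for which no power was claimed, in a 30-patient single-centre trial. All of that stands, and it makes this an efficiency point and not an error.

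Three further limits stand:
- That Baseline enters as a response row and that week 12 is the contrast of interest are inferences. They are the natural reading, but the section states neither.
- The link is left to goodness of fit. With a log or logit link the interaction is on a ratio scale, so it is no longer a raw difference in change and (1+rho)/2 does not carry over. Bounded or skewed outcomes, such as 0-10 ratings or percent area, may well lead there, and their visit variances may differ.
- The size of the gain depends on which analysis is compared with which, as Step 4 shows.

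A reader might infer that the plan forfeits a fixed 6 to 16 points of power. The documents do not support that. The range belongs to one assumed scenario (1 SD, rho 0.7 to 0.3, 14 versus 7, two-sided); a smaller effect or a higher rho falls outside it. Nor do the documents support reading this as a flaw in the primary analysis, which is a pre- versus post-treatment test on lesion counts.

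**Conclusion.** The point holds as an improvement in efficiency, confined to the secondary-outcome mixed models. On the natural reading, with an identity link, equal visit variances and complete data, the planned week-12 contrast is valid but has a larger variance than a baseline-adjusted one for any rho below 1. The direction follows from the formula; the size rests on assumed values. It is worthwhile for a large effect with modest correlation, small for a 0.5-SD effect or a rho of 0.8 or more, and unknown for other links. The change is worth making because it needs no new data, and because the section should in any case name its contrast.

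**What to change.** In Secondary Endpoints, keep the mixed model but constrain the arms to a common baseline mean, with treatment-by-visit terms at weeks 4, 8 and 12. Alternatively, model weeks 4, 8 and 12 as responses with the baseline score as a covariate. The two are similar but not identical under dropout or a non-identity link, so the plan should choose one in advance. State that the between-arm result is the week-12 treatment contrast with its 95% CI, on the scale of whichever link is used.

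The cost is one or two sentences of wording, with the same data, software and number of models. The common-mean version adds only the assumption of equal expected baseline means, which randomisation supplies. The covariate version costs one degree of freedom.

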## **HYPOTHESIS:**

### **Primary Hypothesis:**

1. Subjects treated with Duobrii will experience significant clinical improvement in lesion counts, symptoms associated with AKN as well as minimal dyspigmentation when compared to patients receiving placebo.

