### **Secondary Endpoint**

- Patient reported outcome, improvement in severity of AKN associated symptoms as well as degree of dyspigmentation.

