**Common Reactions:**

- Allergic contact dermatitis
- Application site pain
- Folliculitis
- Skin atrophy
- Excoriation
- Burning
- Pruritus
- Irritation
- Dryness
- Hypertrichosis
- Acneiform dermatitis
- Hypopigmentation
- Perioral dermatitis
- Maceration
- Secondary infection
- Striae
- Miliaria
- Photosensitivity

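### One percent area covers both hypo- and hyperpigmentation with no record of direction, so a flat or falling total could mask new hypopigmentation

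*Combined protocol and SAP*

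**What the plan says.** Under Study Design Overview, the investigator is to "assess the treatment area for any dyspigmentation and document the % area affected within the treatment area at each visit". Under Data Analysis, Secondary Endpoints, the plan adds a comparison of the "percent area of the treatment area affected with dyspigmentation (hypo- or hyperpigmentation) at each visit". Neither place asks for the direction of the change, and the Schedule of Events (Appendix A) has no dyspigmentation row that would supply it.

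Dyspigmentation appears in two roles:

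- **Something that gets better.** The Secondary Endpoint section lists "improvement in severity of AKN associated symptoms as well as degree of dyspigmentation", and the analysis section likewise compares improvement.
- **Something to be kept low.** The Primary Hypothesis expects "minimal dyspigmentation when compared to patients receiving placebo".

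Under Potential Risks, "Hypopigmentation" is among the common reactions to Duobrii, and it is listed again for Bryhali, the rescue product.

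**The concern.** Lightening and darkening are opposite changes. If dark areas present at baseline resolve, that is a benefit. If treated skin becomes lighter than it was, that is a listed reaction to the study products. One percentage that covers both can stay level, fall or rise for reasons that mean different things.

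The two effects would tend to meet in the same arm. Improvement is expected with Duobrii, and so is the listed reaction. The Bryhali requested under Investigational Drug Supply is for 20 subjects, the size of the active arm. Any offset would then act on the active-versus-placebo comparison itself and would not merely add noise to both arms.

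At stake are a secondary endpoint and the pigment part of the hypothesis. Pigment outcomes matter in this trial: the Introduction describes a disease seen mostly in men of African descent, subjects come from a Skin of Color Center, and Amendment 1 added the percent-area measure.

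**Working it through.** **Plan's own figure.** There is none to reproduce. The documents give no baseline area, expected change, standard deviation or power for dyspigmentation.

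**Step 1: the texts side by side.** The visit instruction yields one percentage for any dyspigmentation. The analysis text names both directions within that percentage. The endpoint text expects improvement. The risk lists name hypopigmentation for both products. Read together, they allow benefit and harm to enter one number.

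**Step 2: arithmetic.** Take total = hyperpigmented area + hypopigmented area. This is the natural reading of one percentage for either condition, although no formula is written. The values below are assumed; hypopigmented area starts at 0%.

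| Hyperpigmented | New hypopigmented | Total | Change in total |
|---|---|---|---|
| 20% to 10% | 0% | 20% to 10% | −10 |
| 20% to 10% | 5% | 20% to 15% | −5 |
| 20% to 10% | 10% | 20% to 20% | 0 |
| 20% to 10% | 15% | 20% to 25% | +5 |

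The second row reads as an improvement although 5% of the area is newly lightened. The third reads as no effect. The fourth reads as worsening, although the dark area has halved.

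**Step 3: what this could do to a group comparison.** This is an illustration by simulation: 4,000 runs, two-sided Mann-Whitney test on change from baseline at the 5% level.

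- From the documents: 20 active and 10 placebo; with the 30% dropout allowed for under Sample Size Considerations, 20 × 0.7 = 14 and 10 × 0.7 = 7.
- Assumed: hyperpigmented area falls by a mean of 10 points in the active arm (SD 6) and by 0 on placebo (SD 6). New hypopigmentation in the active arm is 0, or is drawn with mean 5 or 10 points (SD 4) and cut off at zero. There is none on placebo.

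| New hypopigmentation, active arm | Power on total, 20 vs 10 | Power on total, 14 vs 7 |
|---|---|---|
| 0 points | 98% | 91% |
| 5 points | 41% | 29% |
| 10 points | 4% | 4% |

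Hyperpigmented area analysed alone keeps about 98% power with 20 vs 10 and about 90% with 14 vs 7, whatever the hypopigmentation. The 4% is no more than the false-positive rate of the test. The simulated power for hypopigmentation alone is close to 100%, but it carries no weight because placebo was fixed at exactly zero.

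The table shows that the mechanism works at this sample size. It does not show how likely the mechanism is in this trial.

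**The case against.** **No summing rule is written.** A reader might infer that the plan adds the two areas together. The documents do not say so: the bracketed words in the analysis section may only define dyspigmentation, and the case report form is not among the documents. This stands. What the text supports is that one percentage is called for and that direction is not asked for.

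**Direction is not lost altogether.** A reader might also infer that lightening caused by the drug would go unseen for good. That goes too far. Photographs are scheduled at baseline, weeks 4, 8 and 12 and early termination, and could be re-read. Adverse events are collected at every visit, may be found on physical examination, and are defined broadly enough to include new hypopigmentation. What remains is that the listed adverse-event fields contain no area, and neither source is planned for a comparison of direction between arms.

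**The benefit half is only implied.** No section describes dark marks at baseline or predicts that they fade. The word improvement implies some abnormality at baseline, but not its direction or extent. This also stands, and it is why no size can be claimed.

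**A total can be a sensible measure of burden.** If the aim is only to show that little pigment change is present, new hypopigmentation raises the total and counts as harm. That is fair for the wording of the hypothesis. It does not answer the endpoint, which is framed as improvement.

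**It is an added secondary measure.** Percent area is compared in addition to the degree of dyspigmentation. However, no separate instrument for degree is described that would supply direction.

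**Conclusion.** The point holds in a limited form. Following the plan as written can produce a secondary result in which resolving hyperpigmentation and new hypopigmentation offset each other, in part or in full. The recorded percentage alone cannot show that this has happened.

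The conclusion rests on reading one percentage for either condition as their combined area, and on baseline hyperpigmentation that resolves under treatment. The first is the natural reading and the second is implied; neither is stated. The fall in power from 98% to 41% or 4% depends wholly on assumed effects and should not be quoted as an estimate for this trial. The documents do not support saying that cancellation will occur or that harm will go undetected.

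The lesion-count primary analysis is not touched. Because a better method is available at little cost, the change should be made, as an improvement to a secondary measure.

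**What to change.** In Study Design Overview (the paragraph on visits), have the investigator record two figures at each visit: % area hyperpigmented and % area hypopigmented. In Data Analysis, Secondary Endpoints:

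- compare each figure between arms;
- summarise new hypopigmentation by arm, alongside the adverse events already collected;
- keep the combined area as a descriptive total.

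The cost is one extra field per visit and one more comparison in an already long list of secondary analyses. No treatment, visit or sample size changes.

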## **SAFETY MONITORING**

The study will be conducted in accordance with our department's Standard Operating Procedures, which are based on US FDA Title 21 Code of Federal Regulations and ICH Good Clinical Practice guidelines.

An investigator will review all laboratory results and assess for adverse events. The principal investigator will be informed of all adverse events. In the event that a subject's safety is compromised, the investigator will discontinue the subject immediately.

## **POTENTIAL RISKS**

### **Duobri:**

Participants will be advised to avoid a severe sunburn and/or prolonged periods of sunlight exposure. If a sunburn does occur, subjects will be instructed to consult with their

healthcare provider and discontinue Duobrii until sunburn is healed. Hats or other head coverings will be strongly encouraged if direct sunlight exposure is unavoidable.

The following side effects are grouped by likelihood and severity.

**Serious Reactions:**

- HPA axis suppression (prolonged use)
- Cushing syndrome (prolonged use)
- Hyperglycemia (prolonged use)
- Cataracts (prolonged use)
- Glaucoma (prolonged use)
- Intracranial HTN (prolonged use in pediatric patients)

**Common Reactions:**

- Allergic contact dermatitis
- Application site pain
- Folliculitis
- Skin atrophy
- Excoriation
- Burning
- Pruritus
- Irritation
- Dryness
- Hypertrichosis
- Acneiform dermatitis
- Hypopigmentation
- Perioral dermatitis
- Maceration
- Secondary infection
- Striae
- Miliaria
- Photosensitivity

**Bryhali:**

- URI (lotion form)
- Stinging
- Burning
- Pruritis
- Irritation
- Dryness
- Skin atrophy
- Folliculitis
- Hypertrichosis
- Acneiform dermatitis

- Hypopigmentation
- Perioral dermatitis
- Allergic contact dermatitis
- Maceration
- Secondary infection
- Striae
- Miliaria

For further safety information on Duobrii and Bryhali, refer to the respective package inserts.

### **CONTRAINDICATIONS/CAUTIONS:**

**Duobrii:** 1) Hypersensitivity to drug/class/compound 2) Pregnancy 3) Breastfeeding if applied on nipples 4) Female patients of reproductive potential 5) Pediatric patients 6) Skin infection 7) Photosensitivity 8) Sunburn 9) History of skin cancer

**Bryhali:** 1) Hypersensitivity to drug/class/compound 2) Pediatric patients 3) Skin infection

**Definition of an AE:** Any untoward medical occurrence in a subject administered a pharmaceutical product that does not necessarily have a causal relationship with the treatment. An AE can therefore be any unfavorable and unintended sign (including an abnormal laboratory finding), symptom, or disease temporally associated with the use of a medicinal (investigational) product, whether or not considered related to the investigational medicinal product.

Investigational Medicinal Product (IMP) includes the drug under evaluation and the comparator drug(s) if specified as part of the research objective, given at any time during the study. Medical conditions/diseases present before starting the drug of interest are only considered adverse events if they worsen after starting the drug of interest.

The occurrence of adverse events will be sought by non-directive questioning of the patient at each visit during the study. Adverse events also may be detected when they are volunteered by the patient during or between visits or through physical examination, laboratory test, or other assessments. All adverse events will be recorded in the study database including the following information:

1. the severity grade (mild, moderate, severe)
2. its relationship to the drug(s) of interest (suspected/not suspected)
3. its duration (start and end dates or if continuing at final exam)
4. whether it constitutes a serious adverse event (SAE)

A SAE is any untoward medical occurrence that at any dose:

- results in death
- is life-threatening
- requires inpatient hospitalization or prolongation of existing hospitalization
- results in persistent or significant disability/incapacity

- is a congenital anomaly/birth defect
- is otherwise a significant medical event

This includes any SAEs likely to arise from the trial indication or progression of underlying/concomitant illness(es) (e.g. progression of cancer in oncology trials), unless specified in the protocol as study specific exemptions.

Any SAE, irrespective of causality, occurring after the subject has provided informed consent and until four weeks after the subject has stopped study participation must be reported unless otherwise stated in the protocol. SAEs occurring after four weeks from ending study participation should only be reported if considered by the Investigator attributable to the exposure to the investigational drug(s) during the trial period. This includes the period in which the study protocol interferes with the standard medical treatment given to a subject, even if study treatment has not yet started (e.g. withdrawal of previous treatment during washout period, change in treatment to a fixed dose of concomitant medication).

**Timelines:** All serious adverse events (SAEs) from interventional clinical trials must be reported by the sites to the Lead PI within 24 hours of occurrence of the SAE and to the site's own IRB as required. The Lead PI will then report to the manufacturer and any other authorities.

**Follow-up reports:** All related SAEs will be followed until resolution or until it is judged to be permanent, and an assessment will be made at each visit (or more frequently, if necessary) of any changes in severity, the suspected relationship to the drug of interest, the interventions required to treat it, and the outcome.

**Pregnancies:** Any occurrences of a pregnancy in a patient (or a patient's partner) during study participation will be collected. All pregnancies will be followed up to determine outcome, including spontaneous or voluntary termination, details of the birth, and the presence or absence of any birth defects, congenital abnormalities, or maternal and/or newborn complications.

Should a temporary or permanent suspension occur, we would report the occurrence to all appropriate authorities.

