## Appendix A.

### Schedule of Events

	Screening	Baseline	W4	W5 c	W8	W12	W14 d	ET
Visit number	1	1 a	2	3	4	5	6	TBD
Informed consent	X							
Medical History	X							
Demographics	X							
Inclusion/Exclusion	X	X						
Concomitant Medications	X	X	X	X	X	X	X	X
Adverse Events	X	X	X	X	X	X	X	X
Pregnancy Test b	X	X	X		X	X		X
Administer IP		X						
Assess IP Compliance			X	X	X	X		
Return IP						X		X
DLQI		X	X		X	X		X
NRS		X	X		X	X		X
AKN severity		X	X		X	X		X
Clinical Photographs		X	X		X	X		X
Clinical Assessment/ Lesion Count		X	X		X	X	X	X
Tape strips (lesional & non- lesional)		X						
Tape strips (lesional only)						X		

- a. If screening is successful, patient will continue into their Baseline visit on same day.
- b. Where applicable, a urine pregnancy test with high sensitivity to HCG will be performed at screening and at all other visits, prior to dosing female participants of childbearing potential with Investigational Product (IP).
- c. Phone call visit
- d. Follow up visit

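### Listed local reactions such as skin atrophy and striae have no scheduled graded assessment at baseline or follow-up, so painless signs on the back of the scalp may be recorded inconsistently

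*Combined protocol and SAP*

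**What the plan says.** The Study Objective names efficacy and safety together. Potential Risks lists skin atrophy, striae, irritation, dryness and folliculitis among the common reactions to Duobrii, and the Bryhali list contains the same five.

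The adverse event text under Contraindications/Cautions describes how events are found: "The occurrence of adverse events will be sought by non-directive questioning of the patient at each visit during the study". The next sentence adds that events may also be volunteered or may come to light "or through physical examination, laboratory test, or other assessments". Each recorded event gets "the severity grade (mild, moderate, severe" as one of three levels. Conditions present before treatment "are only considered adverse events if they worsen after starting the drug of interest".

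The Study Design Overview requires a directed check of one local reaction: "The investigator will assess the treatment area for any dyspigmentation and document the % area affected within the treatment area at each visit". It also requires symptom surveys covering pain, itch and burning, the DLQI, numerical rating scales, photographs and a lesion count at baseline and weeks 4, 8 and 12.

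Appendix A has a row called "Clinical Assessment/ Lesion Count" at baseline, weeks 4, 8, 12 and 14, and early termination. It has no row for local tolerability.

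**The concern.** The treated site is the occipital scalp, which patients cannot easily see. Itch or burning there will be felt, but thinning skin or striae may not be. An open question is a weak way to find a painless sign that the patient cannot see, and the plan does not ask the investigator to look for one.

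The baseline matters as well. The exclusion criteria rule out intralesional steroids only within 6 months and topical steroids only within 4 weeks, so some participants may enter with skin changes from past treatment. Folliculitis is harder still, because the Introduction describes the disease itself as a scarring folliculitis. Without a graded starting point, deciding whether such a sign is new, worse or old depends on individual judgement.

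With 20 active and 10 placebo participants, local tolerability is the part of the safety objective that the trial can best inform. If the same fraction of cases were missed in both arms, the absolute difference between arms would shrink by that fraction, and the safety summary would look more reassuring than it should.

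**Working it through.** The plan states no figure on this point, so the check sets its sections side by side. For each listed reaction it asks whether a scheduled, scored assessment exists at baseline and later.

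| Listed reaction | Scheduled, scored assessment | Baseline value |
|---|---|---|
| Pigment change | Investigator, % of treatment area (Study Design Overview) | Yes |
| Pain | Symptom survey; 0 to 10 scale (Appendix D) | Yes |
| Itch | Symptom survey; 0 to 10 scale (Appendix D) | Yes |
| Burning | Symptom survey | Yes |
| Skin atrophy | None | Ungraded only |
| Striae | None | Ungraded only |
| Dryness | None | Ungraded only |
| Irritation, as a visible sign | None; overlapping symptoms are surveyed | Ungraded only |
| Folliculitis, as a drug reaction | None; the lesion count measures the disease | Ungraded only |

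Four further checks follow.

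1. **Could the examination route fill the gap?** The adverse event text permits examination findings but does not require a skin check. Appendix A has no physical examination row, and its only laboratory test is for pregnancy. The clinical assessment row has no stated content beyond the count.
2. **Could photographs?** They are scheduled at baseline, weeks 4, 8 and 12, and early termination, for global assessment. No scoring of skin reactions from them is planned, and none are scheduled at week 14, the safety follow-up.
3. **Could the week 5 contact?** It is directed at side effects, but it is a phone call, so the scalp cannot be inspected. Irritation also decides the regimen changes in the Study Design Overview, yet no grade of irritation is recorded.
4. **Does the analysis use such data?** Data Analysis compares dyspigmentation between visits and groups. It plans no tabulation of the other local signs.

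The gap is therefore limited to the last five rows of the table. Dyspigmentation shows that the plan already accepts directed assessment of a local reaction; Amendment 1 added it.

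**The case against.** The strongest defence is that the investigator looks directly at the treated scalp at every in-person visit in order to count lesions. A thinning patch or stria seen then meets the protocol's definition of an adverse event and should be recorded. Safety Monitoring also tells an investigator to assess for adverse events. That stands, and it rules out several stronger readings.

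- A reader might infer that adverse events are sought by open questioning alone. The adverse event text names other routes, the week 5 call discusses side effects, and surveys ask directly about several symptoms.
- A reader might infer that no skin reaction has a baseline value. Dyspigmentation, pain, itch and burning all do, although they are planned as efficacy or patient-reported outcomes and are not linked to adverse event reporting.
- A reader might infer that the worsening rule cannot be applied. The rule does not demand a numeric grade, and medical history, baseline photographs and the baseline assessment give a reference, though an ungraded one.
- A reader might infer that atrophy will be under-recorded by some stated fraction, or that the comparison between arms is biased. The documents give no incidence and no detection rate, and they plan no between-arm test of adverse events. Any figure would be pure assumption.

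Two objections to a form also have weight. The three severity words have no criteria for atrophy or striae, so grades could be arbitrary. Itemising reactions could also give a blinded assessor a hint of the allocation. Both bear on how the form is designed, and the fix allows for them.

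What the defence does not supply is a requirement to look for these signs, a common way to score them, or a recorded starting grade. Looking at the scalp to count lesions does not ensure that different assessors, or one assessor at different visits, note the same signs.

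**Conclusion.** The point holds in limited form. For skin atrophy, striae, irritation as a visible sign, dryness and folliculitis, the protocol schedules no graded assessment at baseline or follow-up. Detection rests on open questioning and on incidental findings at the lesion count, so these signs may be recorded inconsistently, and judging whether they have worsened has only an ungraded reference.

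No size can be attached. The conclusion rests on the listed reactions, the wording of the adverse event text and the rows of Appendix A. It also rests on one judgement that the documents do not test: that painless signs on the back of the scalp are less reliably noticed without a directed check. Nothing here contradicts another part of the plan or affects the primary endpoint. It is a cheap improvement to how the safety objective is served.

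**What to change.** Define the content of the existing clinical assessment row in Appendix A. At baseline, weeks 4, 8, 12 and 14, and early termination, the investigator records skin atrophy, striae, irritation, dryness and folliculitis at the treated site as none, mild, moderate or severe. These are the adverse event section's own three levels plus none. Give each grade a one-line descriptor so that the levels mean the same thing across visits and assessors. Complete the form only after the lesion count has been recorded.

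State in the adverse event section that a new sign, or a worsening from the baseline grade, is entered as an adverse event. Add to Data Analysis a descriptive table of change from baseline by arm, with no test.

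The cost is one short form and a few minutes at visits already scheduled, with no extra staff, visit or procedure. A small risk remains that itemised reactions hint at allocation. Recording the count first keeps the form from influencing that visit's count, though not the impression carried to later visits.
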